Patients with a history of stroke who are admitted to, or attending follow-up at, University Malaya Medical Centre (UMMC) during the study period will be screened for eligibility. Eligible patients will be approached and provided with detailed information about the study and invited to participate. In addition, public advertisements (posters and flyers within UMMC) will be used to increase awareness of the study and facilitate recruitment. Patients who meet the inclusion criteria and agree to participate will be enrolled only after providing written informed consent.

Following enrolment, all participants will be allocated to either an intervention group or a control group in a 1:1 ratio. To ensure that there are exactly 20 patients in both the control and intervention groups, block randomization will be used using a random number generator. After randomization, the group assignments will be kept in a password-protected file that only the study coordinator can access. The assessor will not have access to this information because the patients will be labelled with anonymous codes that do not reveal whether they are in the control or intervention group. The assessor will only know the code, not the group assignment, ensuring unbiased evaluation.

A certified music therapist will prescribe the intervention and train the patients and caregivers before the start of the home-based music therapy. A trained assessor will evaluate the cognition at baseline, and also the outcome. The assessor is blinded to the patients' allocation group and will evaluate the cognitive outcomes at baseline, immediately after completion of the intervention period at four weeks and at 3 months post intervention.

Intervention group

The music therapy session described follows a structured and engaging approach, aimed at enhancing the patient's cognitive skills. Here's a summary of the session components:

Intervention Group: Home-Based Music Therapy Rehabilitation Program

1. Song Materials and Levels

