2. **Memory Aids:** Tools like mnemonic strategies, repetition tasks, and external memory aids (e.g., calendars, notes) help rebuild short-term and working memory.
3. **Executive Function Training:** Targeting skills such as problem-solving, planning, and organizing tasks through structured exercises, gradually improving independent thinking.
4. **Communication and Language Therapy:** Speech-language pathologists work with patients to improve verbal and non-verbal communication, focusing on both comprehension and expression.
5. **Problem-Solving Exercises:** These help patients break down real-life problems into smaller, manageable steps, encouraging better decision-making skills.

Both the intervention and control groups will continue receiving the standard care

Figure 1. Eight-Tone Desk Bell

[figure not shown]

Figure 2: Finale Music Software User Interface

Inclusion Criteria:

1. Diagnosed with ischemic or haemorrhagic stroke confirmed by CT scan
2. Duration of stroke within the first one year
3. Age 18 – 70 years old
4. Ability to provide informed consent
5. Understands Bahasa Melayu or English with basic communication abilities to follow instructions during therapy sessions
6. Mild to moderate cognitive impairments with MoCA score of 10-25, with incomplete score for the attention sections
7. Availability of caregiver (formal or informal) who can assist in the music therapy, monitor and give feedback during the music therapy sessions at home
8. Have one normal functioning hand to perform the movements during the music therapy rehabilitation program
9. Have good balance and able to sit upright

Exclusion Criteria:

1. Severe aphasia
2. Significant uncorrected hearing or visual impairments preventing engagement in music therapy.
3. Severe or unstable medical conditions (e.g., uncontrolled hypertension or diabetes).
4. Medications that significantly impair cognition or motor function (e.g., high-dose sedatives).
5. History of neurological diseases other than stroke (eg, Parkinson's disease).

Outcome measures

This will be assessed at baseline, after completion of 4-week sessions and also at 3 months after completion. Primary outcome measures are Montreal Cognitive Assessment (MoCA), Trail Making Test (TMT A and B), Digit Span (Forward and Backward) and Clock Drawing Test (CDT). The secondary outcome measure is computer-based Cogniplus software for Reaction Time and Attention tests

Sample size calculation:

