A sample of 40 subacute stroke patients (18 control and 18 intervention) within the first one year post-stroke, will be recruited from UMMC. This number is chosen based on practical considerations to evaluate feasibility metrics and exploratory analysis as in the objectives. For these purposes, a sample size of 36 is typically adequate to gather enough information about the practical aspects of the trial. This number could also ensure that the feasibility objectives are met even with at least 20% dropouts. This total number of 36 will be sufficient within the study period and the grant duration.

Statistical Analysis:

Descriptive Statistics and Exploratory Inferential Statistics will be used in this study.

The means, standard deviations, and 95% confidence intervals (CIs) for cognitive outcome measures (e.g., memory, attention, executive function scores) at baseline, post-intervention, and follow-up will be used. This will provide a preliminary understanding of the data distribution and effect sizes.

For the exploratory Inferential Statistics, independent t-test (or Mann-Whitney U Test) will be used to compare the mean changes in cognitive scores between the intervention and control groups. The independent t-test if the data are normally distributed. If not, we will use the Mann-Whitney U test as a non-parametric alternative.

Within each group, we will compare the baseline and post-intervention scores using the paired t-test for normally distributed data or the Wilcoxon signed-rank test for non-parametric data. Cohen's d will be used for independent t-tests (between groups) or r for non-parametric tests.

A repeated measures ANOVA (if the data is normally distributed) or a mixed-effects model will be used to explore changes over time (baseline, post-intervention, and follow-up). Given the small sample size, these analyses will likely be underpowered but can provide estimates of variability and preliminary trends.

RESEARCH DATA

Where will the data be kept?

The demographic data of the patients, and data on cognitive performance and other relevant data will be kept in a dedicated research file and hard drive. The files are in the laptop will be secured with password and the notes will be kept in a locker in the Department of Rehabilitation Medicine, Faculty of Medicine with one of the co-researchers.

Anonymity of data

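### Comparing the arms on raw change scores is valid, but less precise than adjusting for the baseline score the trial already collects

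*Protocol*

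**What the plan says.** The Statistical Analysis section of the protocol fixes both the test and the scale: an "independent t-test (or Mann-Whitney U Test) will be used to compare the mean changes in cognitive scores between the intervention and control groups". The t-test applies if the data are normal, the Mann-Whitney test if not. For effect size, "Cohen's d will be used for independent t-tests (between groups) or r for non-parametric tests". No covariate is named.

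The baseline scores exist. Of the outcome measures, the protocol says: "This will be assessed at baseline, after completion of 4-week sessions and also at 3 months after completion". The measures are MoCA, Trail Making A and B, Digit Span, the Clock Drawing Test and the computer-based attention tests.

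Patients are "allocated to either an intervention group or a control group in a 1:1 ratio" by block randomisation, and no stratification by baseline score is described.

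A repeated measures ANOVA or mixed-effects model is also planned, to explore change over the three visits. There, baseline is one of the time points. The section on expected preliminary cognitive outcomes says the results should supply effect size estimates for larger trials. The Statistical Analysis section adds that the analyses can give estimates of variability.

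**The concern.** A change score subtracts the whole baseline score, which amounts to assuming that follow-up rises one for one with baseline. When the true slope is below 1, the subtraction goes too far. The arm that happens to start worse then appears to gain more, by regression to the mean. Estimating the slope instead of fixing it at 1 removes that dependence and usually narrows the confidence interval.

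No efficacy claim depends on this. What is at stake is the quality of the between-group estimates that are meant to inform the next trial. With arms this small, a chance baseline difference of some size is to be expected, and precision is scarce.

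**Working it through.** **Inputs.** The arm size is stated inconsistently. The sample size section has "A sample of 40 subacute stroke patients (18 control and 18 intervention" (18 + 18 = 36), while the Study design section wants "exactly 20 patients in both the control and intervention groups". I use 18 per arm and check other sizes below. The protocol gives no power calculation, SD or rho, so there is no planned figure to reproduce. Rho is assumed over 0.3 to 0.9, with equal SDs (s) at baseline and follow-up.

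**Precision.** For the difference between arms with n per arm:
- Change score: variance = (2/n) × 2(1 − rho)s².
- ANCOVA with known slope: variance = (2/n) × (1 − rho²)s².
- Ratio = (1 − rho²) / [2(1 − rho)] = (1 + rho)/2.
- Cost of estimating the slope: factor 1 + 1/(2n − 4) = 1 + 1/32 = 1.031 at n = 18. Error degrees of freedom fall from 34 to 33.

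| Assumed rho | (1 + rho)/2 | × 1.031 | 95% CI narrower by |
|---|---|---|---|
| 0.3 | 0.65 | 0.67 | 18% |
| 0.5 | 0.75 | 0.77 | 12% |
| 0.7 | 0.85 | 0.88 | 6% |
| 0.9 | 0.95 | 0.98 | 1% |

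At rho 0.5 the half-widths of the 95% CI are 0.677 SD (change score) and 0.596 SD (ANCOVA). A change-score analysis would need about 36/0.773 = 46.5 patients to match ANCOVA with 36.

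**Break-even.** Setting 1.03125 × (1 + rho)/2 = 1 gives rho = 2/1.03125 − 1 = 0.94. At 14 per arm (18 × 0.8 = 14.4 after 20% dropout) the factor is 1 + 1/24 = 1.042 and the break-even is 0.92.

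**Other arm sizes.** At rho 0.5 the ratio is 0.75 × 1.042 = 0.78 with 14 per arm and 0.75 × (1 + 1/36) = 0.77 with 20 per arm. The conflict over arm size does not alter the conclusion.

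**Chance imbalance.** At 18 per arm the baseline difference has standard error √(2/18) = 0.33 SD, and the chance of a difference above 0.5 SD in either direction is about 13%. Given a difference d, the change-score estimate is shifted by −(1 − rho)d. For d = 0.5 SD that is −0.25 SD at rho 0.5 and −0.15 SD at rho 0.7.

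**Simulation.** In 20,000 trials at 18 per arm, the variance ratios were 0.776 (rho 0.5) and 0.876 (rho 0.7). The change-score estimate moved with the imbalance at slopes of −0.50 and −0.30, the ANCOVA estimate at 0.00. These agree with the formulas.

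**The other planned model.** With complete data, the group-by-time contrast of a repeated measures ANOVA, taken from baseline to a follow-up visit, is the same change-score comparison. It does not supply the adjustment.

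**The case against.** The strongest reply is that little depends on this test. The protocol makes feasibility its focus, calls these analyses exploratory and probably underpowered, and attaches no decision to them. That stands and limits the point to a modest one.

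The gain also rests on assumptions. MoCA at entry is restricted to 10–25 and follow-up is not, so the SDs may differ. With a follow-up SD 1.25 times baseline and rho 0.8, the slope is 0.8 × 1.25 = 1 and the change score loses nothing. That stands as well.

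The mixed model's terms are not given, and one that constrained the arms to equal baseline means would give essentially the ANCOVA adjustment. But no such constraint is stated, and the named between-group comparison remains the change-score test.

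A reader might infer more than the documents support:
- **That imbalance is left uncorrected, or that the test is biased.** Baseline is subtracted in full, so the imbalance is over-corrected. Over all randomisations the estimate is unbiased.
- **That the imbalance shift is a second harm on top of lost precision.** It is the same loss. At rho 0.6, 18 per arm and known slope, the variances are 1.6/18 = 0.0889 and 1.28/18 = 0.0711. The gap of 0.0178 equals (0.4 × 0.333)² = 0.133².
- **That Cohen's d from this trial could not be used later.** If d is standardised by the SD of change, it differs from d on the score by 1/√(2(1 − rho)), which is 1.12 at rho 0.6 and 1.58 at 0.8. But the protocol does not name the denominator, and it reports means and SDs at each visit, so the difference can be re-standardised.
- **That time since stroke must be a covariate.** "Duration of stroke within the first one year" is an entry criterion. Nothing in the protocol shows that it predicts these scores, and a covariate that adds nothing costs precision: with two covariates the factor is 1 + 2/31 = 1.065, so at rho 0.8 the ratio is 0.90 × 1.065 = 0.96.

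**Conclusion.** The point holds as a matter of efficiency. The protocol commits to a valid comparison that, for any rho below about 0.94 at 18 per arm with equal SDs, has larger variance than one adjusted for the baseline already in hand. The benefit of changing runs from an 18% narrower confidence interval at rho 0.3 to 1% at rho 0.9. It vanishes if the true slope is near 1, and the documents give no figure that would place the trial within this range. The change is worth making because the estimates are intended for planning a larger trial, but it does not threaten the feasibility conclusions.

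**What to change.** Make the main exploratory between-group estimate an ANCOVA of each follow-up score on arm and that outcome's own baseline score, at four weeks and at three months after completion. Report the adjusted mean difference with its 95% CI. If it is standardised, name the SD used.

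Transform skewed Trail Making times, at baseline and follow-up alike, before fitting. For skewed or short bounded scores such as the Clock Drawing Test, use rank-based ANCOVA in place of the Mann-Whitney test. Linear ANCOVA should not be imposed on every outcome.

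Time since stroke need not be added.

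No new data are required. The statistical cost is one error degree of freedom and about 3% variance inflation from estimating the slope. The text change is a few sentences in the Statistical Analysis section, best made before outcome data are seen.

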It is expected that the home-based music therapy rehabilitation programme will demonstrate acceptable feasibility among stable stroke survivors in Malaysia. This includes achieving satisfactory recruitment and retention rates, good adherence to the prescribed intervention, and positive participant-reported satisfaction. These outcomes will indicate that the programme is acceptable and practicable for implementation in a home setting within the local context.

2. Preliminary Cognitive Outcomes

The study is expected to show trends toward improvement in attention and processing speed following participation in the home-based music therapy rehabilitation programme, as measured by standardized cognitive assessment tools. While the study is not powered to determine definitive efficacy, the findings will provide preliminary data on potential cognitive benefits and inform the selection of outcome measures and effect size estimates for future larger-scale trials.

3. Safety and Practicality

The intervention is expected to be safe, with minimal or no adverse events related to participation. It is anticipated that participants and caregivers will be able to implement the programme with minimal difficulty, demonstrating adequate compliance with the prescribed activities. These findings will support the practicality of delivering a structured music therapy rehabilitation intervention in a home-based setting.

METHODOLOGY

Study design

This study will adopt a prospective, single-centre, randomized controlled feasibility study design with two parallel groups: an intervention group receiving music therapy in addition to standard neurorehabilitation, and a control group receiving only standard neurorehabilitation. The primary focus is to evaluate the feasibility, acceptability, and safety of a structured home-based musical rehabilitation programme for cognitive rehabilitation after stroke. Secondary objectives include exploration of preliminary effects on attention and processing speed.

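### Within-group paired tests carry no limit on how they are read and can be significant without any effect of music therapy; statements about effect should rest on the planned between-arm comparison

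*Protocol*

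**What the plan says.** The Statistical Analysis section opens with "Descriptive Statistics and Exploratory Inferential Statistics will be used in this study". It plans descriptive summaries, then an independent t-test or Mann-Whitney test that "will be used to compare the mean changes in cognitive scores between the intervention and control groups". The next paragraph adds a second kind of test: "Within each group, we will compare the baseline and post-intervention scores using the paired t-test for normally distributed data", or the Wilcoxon signed-rank test otherwise. Nothing says how a within-group result is to be interpreted.

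Under Expected outcomes, item 2 (Preliminary Cognitive Outcomes), the protocol states "The study is expected to show trends toward improvement in attention and processing speed following participation". The control group is not mentioned there. The same item says that the study is not powered for definitive efficacy and that its results will inform outcome selection and effect sizes for later trials.

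Entry requires "Mild to moderate cognitive impairments with MoCA score of 10-25, with incomplete score for the attention sections", and the MoCA is also listed among the primary outcome measures. Both arms continue standard care, whose typical components, listed under Control Group: Standard Care, begin with attention training.

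**The concern.** Objective 2 is about the preliminary effects of the music programme. A paired test in one arm asks something else: whether scores changed from baseline, for any reason. The protocol itself describes several reasons that apply to both arms:

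- recovery within the first year after stroke;
- background rehabilitation aimed at the same domain as the outcomes;
- familiarity with the tests on second administration;
- for the MoCA, some upward regression, because patients enter on a restricted range of scores.

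A gain in the music arm from any of these would meet the expected result as worded. A report that the music arm changed significantly and the control arm did not could also be taken for a treatment effect, although it does not compare the arms. If such a result were carried into planning a larger trial, it would rest on change that the control arm was included to remove.

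**Working it through.** **The plan's own figure.** There is no power, alpha, SD or expected change to reproduce. The number per arm is inconsistent: Sample size calculation has "A sample of 40 subacute stroke patients (18 control and 18 intervention) within the first one year post-stroke", and 18 + 18 = 36; Study design has "To ensure that there are exactly 20 patients in both the control and intervention groups", and 20 + 20 = 40. That is a separate matter. Both values are used below and the conclusion is the same.

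**Inputs.** n = 18 or 20 per arm (protocol). Two-sided alpha of 0.05 (assumed, in line with the planned 95% CIs). Standardised change d = mean change / SD of change, equal in both arms, so that the treatment effect is zero (assumed range; the documents give none).

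**Within-arm test.** Under a change of d, the paired t statistic follows a noncentral t with n − 1 degrees of freedom and noncentrality d√n. For n = 18, √18 = 4.243, so d = 0.2, 0.3, 0.5 and 0.8 give noncentralities of 0.849, 1.273, 2.121 and 3.394. Let p be the chance of significance. With independent arms and identical true change, the chance that the intervention arm is significant and the control arm is not is p(1 − p).

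| d in both arms | p, n = 18 | p(1 − p), n = 18 | p, n = 20 | p(1 − p), n = 20 |
|---|---|---|---|---|
| 0 | 0.050 | 0.048 | 0.050 | 0.048 |
| 0.2 | 0.126 | 0.126 × 0.874 = 0.110 | 0.136 | 0.136 × 0.864 = 0.118 |
| 0.3 | 0.225 | 0.225 × 0.775 = 0.174 | 0.247 | 0.247 × 0.753 = 0.186 |
| 0.5 | 0.516 | 0.516 × 0.484 = 0.250 | 0.565 | 0.565 × 0.435 = 0.246 |
| 0.8 | 0.892 | 0.892 × 0.108 = 0.096 | 0.924 | 0.924 × 0.076 = 0.070 |

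The discordant pattern cannot exceed 25%, the maximum of p(1 − p), and it falls again when drift is large because both arms become significant.

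**Between-arm test.** Shared drift cancels: (drift + effect) − drift = effect. In 20,000 simulated trials per setting with zero effect, the independent t-test on change rejected in 0.048 to 0.051 of trials at d = 0, 0.3, 0.5 and 0.8, for n = 18 and n = 20.

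**Regression to the mean on the MoCA.** Scores were simulated with selection to 10–25, taking the selection score as baseline. Assumed population mean/SD were 20/5, 22/4 and 24/4, and test-retest reliability 0.7 to 0.9. Selection alone raised the retest mean by 0.1 to 0.7 points, and the paired test was significant in 5% to 17% of trials. Adding an assumed 1-point gain from recovery or practice gave 29% to 84%. Adding 2 points gave 69% to nearly 100%.

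**The case against.** A reader might infer that the protocol treats a significant within-arm test as proof that the therapy works, or would read significance in one arm only as an effect. The documents do not support that: no sentence says either. A paired test is a valid test of change, which is all the section asks of it. The between-arm test of change comes first in the same section, Cohen's d is tied to it, and Control Group: Standard Care says the control arm is there for comparison. The inferential statistics are called exploratory, and the study's main focus is feasibility, acceptability and safety. All of this stands, and it limits the impact.

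A reader might also infer that drift will make the paired tests positive. The documents give no size of drift, and the chance of significance runs from about 5% to nearly 100% over the assumed values. Selection on low scores is a weak contributor by itself. It acts directly only on the MoCA and its attention items; Trail Making, Digit Span and Clock Drawing are affected only through correlation. It is smaller still if the screening and baseline MoCA are separate measurements, which the protocol does not settle. The quoted test also uses only two of the three assessments, so practice enters once.

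What the objection does not remove is that the tests are planned without any limit on their reading, next to an expectation that a within-arm gain would satisfy. Calling an analysis exploratory or underpowered warns about imprecision. It does not warn that the test can be positive for reasons unrelated to the therapy.

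**Conclusion.** The point holds in a limited form. The within-group tests cannot separate music therapy from change shared by both arms, and nothing in the protocol limits how they are read. With no treatment effect and an assumed equal change of 0.2 to 0.8 SD, they would be significant in about 13% to 89% of trials at 18 per arm. The intervention arm alone would be significant in about 10% to 25%. These figures illustrate the mechanism; they do not predict this trial, and they rest on the assumed drift and an assumed two-sided 0.05. The between-arm test that is already planned keeps its error rate near 5%. Because that test is in place and the work is declared exploratory, this is an inexpensive improvement to the plan and does not invalidate the design.

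**What to change.** In Statistical Analysis, replace the within-group paired t and Wilcoxon tests with descriptive within-arm change: mean change, SD and 95% CI, without a p-value. Add one sentence saying that any statement about preliminary effect rests on the between-arm difference in change with its 95% CI. That sentence matters most, since a within-arm interval carries much the same information as the paired t-test and needs the same limit on its reading.

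In Expected outcomes, item 2, word the cognitive result relative to the control group. This can be put as estimating the difference from control, so that a feasibility study does not appear to predict efficacy.

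The cost is two short edits and the loss of within-arm p-values. No extra data or patients are needed.

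### A normality check decides whether each cognitive measure is reported as Cohen's d or as r, so the effect estimates meant for later trials can end up on different scales

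*Protocol*

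**What the plan says.** Under Expected outcomes, item 2 (Preliminary Cognitive Outcomes), the protocol says that the study lacks power for definitive efficacy but that its findings will "inform the selection of outcome measures and effect size estimates for future larger-scale trials".

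The Statistical Analysis section sets out how the effect is obtained:

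- **Contrast.** The aim is to "compare the mean changes in cognitive scores between the intervention and control groups". No baseline adjustment is mentioned for this comparison.
- **Choice of test.** "The independent t-test if the data are normally distributed. If not, we will use the Mann-Whitney U test as a non-parametric alternative". The section does not say how normality is judged, on which quantity, or in which arm.
- **Effect size.** "Cohen's d will be used for independent t-tests (between groups) or r for non-parametric tests".
- **Intervals.** "The means, standard deviations, and 95% confidence intervals (CIs) for cognitive outcome measures" (memory, attention and executive function scores are the examples given) "at baseline, post-intervention, and follow-up will be used". The section adds: "This will provide a preliminary understanding of the data distribution and effect sizes".

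No interval is named for the between-arm difference in change, for d or for r.

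The Outcome measures section lists MoCA, TMT A and B, Digit Span Forward and Backward, and the Clock Drawing Test as primary measures. That is six scores. The Cogniplus reaction time and attention tests are secondary.

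**The concern.** Choosing among outcome measures for a later trial needs all of them on one scale. Here the scale is itself a result of the data. A measure that passes the check yields a standardised mean difference; one that fails yields a rank-based coefficient. The two have different ranges and meanings, and only the first enters a sample-size formula for means directly. In small arms the check also responds to chance, to mild skew and to the coarseness of integer scoring, none of which says how well a measure detects a treatment effect.

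The planned intervals do not fill the gap. An interval for a mean at one visit says nothing direct about the difference between arms in change. Without that interval, a reader of the results could take the d or r at face value when planning the next study.

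**Working it through.** **Inputs.** Arm size: 18, from Sample size calculation ("A sample of 40 subacute stroke patients (18 control and 18 intervention"). Study design gives 20 per arm, so I also show 20, and 14 for roughly 20% dropout from 18. The protocol gives no normality test, definition of r, alpha, power or SD. Assumed for illustration: Shapiro-Wilk at 5% in each arm, r = Z/√N, two-sided 5%, 80% power, and an observed d of 0.5. The protocol's sample size is pragmatic, so it has no power figure to reproduce.

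**1. How often the scale switches (18 per arm, simulated).**

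- Truly normal outcomes: two checks at 5% give 1 − 0.95² = 0.0975; simulation gives about 10%.
- Changes between two skewed scores (gamma shape 4, within-person correlation 0.5): about 20 to 25%, depending on how the correlation is built in.
- Normal changes rounded to whole points, as with integer-scored tests: about 26% at SD 2, 46% at SD 1.5 and 88% at SD 1. These SDs are assumptions.

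Taking the six primary scores at one time point, and treating the six checks as independent for illustration, the chance that at least one moves to r is 1 − 0.90⁶ = 47% if all are normal, and 1 − 0.80⁶ = 74% at a 20% switch rate. Scores from the same patients are correlated, so these two figures are only indicative.

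**2. What the switch does to the number.** In simulated normal data with 18 per arm, a true d of 0.5 goes with a mean r of about 0.24. With n per arm = 2(1.960 + 0.842)²/d² = 15.70/d²:

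- d = 0.5: 15.70/0.25 = 62.8, so 63 per arm.
- r = 0.24 converted by d = 2r/√(1 − r²) = 0.48/0.971 = 0.494: 15.70/0.244 = 64.3, so 65 per arm.
- 0.24 misread as d: 15.70/0.0576 = 272.5, so 273 per arm.

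The conversion works here because the data are normal. The r branch is reached when the data have been judged not to be.

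**3. Why the planned intervals do not give the contrast.** With equal SD s at both visits, the SD of change is s√(2(1 − ρ)), where ρ is the within-person correlation: 1.26s at ρ = 0.2, 1.00s at 0.5 and 0.63s at 0.8. Means, SDs and intervals by visit do not determine ρ, so the between-arm interval cannot be recovered from them.

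**4. How imprecise the observed effect is.** For d = 0.5 and 18 per arm, t = 0.5 × √(18/2) = 1.5 on 34 degrees of freedom. The exact noncentral-t 95% interval is −0.17 to 1.16. It is −0.26 to 1.25 at 14 per arm and −0.13 to 1.13 at 20. At the upper limit for 18 per arm, a later trial would need 15.70/1.16² = 11.7, so 12 per arm; the lower limit is below zero and gives no finite size.

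**5. Change score against baseline adjustment.** With equal variances, the change-score contrast has variance proportional to 2(1 − ρ) and the ANCOVA contrast to 1 − ρ². The ratio of ANCOVA to change is (1 + ρ)/2, which is 0.75 at ρ = 0.5. The gain uses data already collected.

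**The case against.** - **The interval may be in the SAP.** An unseen SAP could add it, and a t-test on changes normally comes with one. This stands, so the missing interval is the softer half of the point. The switch between d and r is different: the protocol itself fixes it.
- **Pairing d with the t-test and r with the Mann-Whitney test is conventional.** True for reporting one outcome. It does not serve a stated wish to compare measures with each other.
- **Other information is planned.** Means and SDs are to be given at each visit, a repeated measures ANOVA or mixed-effects model is planned, and r converts roughly to d. So the later trial would not depend on a single bare number. But the protocol attaches its effect size only to the two-group tests, and the conversion leans on near-normality.
- **The wide interval comes from the small sample.** This stands in full. One scale and a printed interval would leave it as wide; they would only make it visible. The protocol already says these analyses are likely underpowered.
- **Switch rates depend on assumptions.** Also true. A check on raw gamma (shape 4) scores flags about 45%, but the protocol compares changes, so that figure does not apply here.

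A reader might infer that the next trial will be sized on the observed d. No section says so; the protocol speaks only of informing effect size estimates.

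**Conclusion.** The point holds in limited form. The protocol ties the effect scale to an unspecified normality check on unadjusted changes, and this works against its own aim of informing outcome selection and effect size estimates. Under the assumed Shapiro-Wilk check with 18 per arm, the switch to r affects about 10% of truly normal outcomes and about 20 to 25% of moderately skewed changes, with higher rates for coarse integer scores.

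It would go too far to say that no intervals are planned, that r cannot be converted at all, or that the switch causes the imprecision of −0.17 to 1.16. Intervals by visit are planned, r converts approximately, and the imprecision is due to sample size. The conflict between 40 and 18 + 18 in the sample-size section is a separate matter and does not change this conclusion.

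The importance is minor to moderate: the analysis is exploratory, and no decision within this trial rests on d or r.

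**What to change.** In Statistical Analysis:

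1. Drop the normality switch, and drop r as the basis for the effect estimate.
2. For every cognitive measure, whatever its distribution, report the baseline-adjusted (ANCOVA) between-arm mean difference in test units with its 95% interval (bootstrap if skewed) and the SD.
3. Give d with its 95% interval as a supplement, and name the SD used to standardise it.
4. Keep the Mann-Whitney test, if wanted, as a sensitivity analysis.

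In Expected outcomes, item 2, add that the observed effect size is imprecise because of the sample size (for example, d = 0.5 has a 95% interval of about −0.17 to 1.16 at 18 per arm) and will not by itself size a later trial.

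The cost is analysis wording only, with no new data or visits. The change is best made before any outcome data are seen, so that the choice of scale cannot appear driven by results.
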